4.4.2.6 Immunogenicity

Anti-imlifidase antibody at 1, 2, and 3 years after start of treatment in the feeder trial, will be listed and summarised.

4.5 Safety

Safety parameters will be evaluated for the FAS (which in this study is the same as the safety analysis set).

4.5.1 Adverse events

Adverse events (AEs) will be classified according to the Medical Dictionary for Regulatory Activities (MedDRA version 23.1).

4.5.1.1 Adverse Event

An AE is the development of an undesirable medical condition or the deterioration of a pre-existing medical condition following or during exposure to a pharmaceutical product or trial procedure. No IMP will be administered in this trial and only AEs that the investigator judges as related to IMP administered in the feeder trial, and adverse events caused by a procedure in the protocol (such as blood sampling) will be captured and reported in this trial.

An AE overview summary table will be prepared including the number of patients reporting an AE, the percentage of patients (%) with an AE, and the number of events (E) reported for the following categories:

- All AEs
- AEs – by System Organ Class (SOC) and Preferred Term (PT)
- AEs – by causality

- AEs – by severity
- Serious AEs (SAEs)
- Serious AEs (SAEs) – by causality
- Serious AEs (SAEs) – leading to death
- Serious AEs (SAEs) – leading to withdrawal

Data listings will be provided for:

- All AEs sorted by patient number
- All AEs sorted by MedDRA SOC and PT
- SAEs

5 Interim analyses

No interim analyses were performed.

6 Deviations from protocol analysis

The study was terminated prematurely in January 2023 due to an internal decision that will allow Hansa to focus on prioritised projects and allocate resources in the way the company deems most effective according to its strategic priorities.

7 Quality control

The quality control of the data will be performed as follows:

- By Data Management for all CRF data following the data validation plan
- By Statistics and Programming for all data received

The QC depends on the process below, but it will follow █ SOP 703 Single Use Programs:

SDTM data sets will be generated by programs in the Statistical analysis system (SAS) by reading in lab data and export data to SDTM formats following the SDTM specifications. The QC will include:

- Independent Code review
- CRF annotation review vs SDTM content
- Run of Pinnacle verification
- QC of CRF input vs output in SDTM on a sample of data
- Format and fonts in annotated CRF

ADaM data sets will be based on the SDTM data sets. The programming of the ADaM datasets will be performed in SAS and QC of the programs will include

- Independent code review
- Run of Pinnacle verification
- QC of SDTM input data vs output in ADaM or listings

Tables, listings and figures (TLF) will be created by SAS programs and based on the ADaM data sets. The programming of TLFs will be reviewed by an independent person.

Since there are no formal statistical analyses, double programming will not be applied in this study.

The programming and execution of programs for producing data sets and tables, figures and listings follow the █ SOPs 701, 702 and 703 on standard programs, programming environment and single use programs respectively.

SAS Viya version 03.05 will be used for data handling and presentation.

8 Layout of output

The output will follow █ standard output templates. Tables and listings will first be prepared as individual RTF (Rich text format, which is a standard text format) files. This file type may be opened and saved in the currently available Microsoft Word versions. Graphical output will be prepared in PNG (Portable network graphics) format, which is the standard graphical format in current Microsoft software packages and therefore easily importable into Microsoft Word documents.

Tables and figures will per default be created in portrait format while listings will be in landscape format. Margins and font will be chosen to respect the requirements for filing with EMA (European medicines agency) and FDA (the US Food and drug administration).

The output items (tables, listings, figures) will be collected in Word documents. Separate Word documents will be created for tables, figures, and listings, respectively.

9 Tables, listings and figures

The following sections contains lists of the tables, figures and listings (TLF) which will be produced.

9.1 Tables

Table 14.1.1 Patient disposition, including reason for discontinuation (All screened patients).

Table 14.1.2 Protocol Deviations (FAS).

Table 14.1.3 Demography and body measurements (FAS).

Table 14.1.4 Medical and surgical history (FAS).

Table 14.1.5 Concomitant medication (FAS).

Table 14.1.6 Previous transplant kidney history (FAS).

Table 14.2.1 MFI levels for DSA – by time point (FAS).

Table 14.2.2 Kidney function (based on S/P-creatinine analysis) (FAS).

Table 14.2.3 Proportion of patients with absence of graft loss at 1 year, 2 years and 3 years (FAS)

Table 14.2.4 Proportions of patients with presumed or biopsy proven AMR episodes (FAS).

Table 14.2.5 Proportion of patients with presumed or biopsy-proven rejection episodes, (other than AMR episodes) (FAS).

Table 14.2.6 Total IgG – by timepoint (FAS).

Table 14.2.7 Proportion of patients having reduction in total IgG (FAS).

Table 14.2.8. Patient survival (FAS)

Table 14.3.1 Overview of AEs (FAS).

Table 14.3.2 Summary of AEs – by SOC and PT (FAS).

Table 14.3.3 Summary of AEs – by causality (FAS).

Table 14.3.4 Summary of AEs – by severity (FAS).

Table 14.3.6 Summary of SAEs (FAS).

Table 14.3.7 Summary of SAEs – by causality (FAS).

Table 14.3.10 Summary of SAEs leading to death (FAS).

Table 14.3.11 Summary of SAEs leading to withdrawal (FAS).

Table 14.4.1 Summary of clinical chemistry variables (U-Albumin, Creatinine, U-Albumin/creatinine ratio) – by time point (FAS).

Table 14.4.2 Anti imlifidase IgG (ADA) (mg/mL) – by time point (FAS)

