4.4.1 Primary efficacy analysis

Overall graft survival at Year 3. Graft survival is defined as time from start of treatment (imlifidase or plasma exchange) of active or chronic active AMR in feeder trial to graft loss. Graft loss is defined as permanent return to dialysis for at least 6 weeks, re-transplantation, or nephrectomy. If dialysis is used to define graft loss, the date of graft loss will be the first day of the last ongoing dialysis period reported.

The primary endpoint, overall graft survival at Year 3, will be analysed by the Kaplan-Meier survival method. The overall graft survival will be tabulated and presented graphically by treatment.

The following events will be censored at the time of occurrence: withdrawal from the trial without graft loss, evaluation time point and end of trial without graft loss.

The reason for graft loss will be tabulated by time.

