4.4.2 Secondary efficacy analyses

4.4.2.1 Graft survival at Year 1 and 2

Graft survival at Year 1 and Year 2 will be listed by patient and summarized by treatment and time point and analysed using the same methods as for the primary efficacy analysis .

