9.3 Figures

Figure 14.2.1 Individual plots DSA (including sum of DSA) vs time (FAS).

Figure 14.2.2 Mean plots of sum of DSA vs time (FAS).

Figure 14.2.3 Individual Anti-imlifidase IgG (ADA) vs time (FAS).

Figure 14.2.4 Mean Anti-imlifidase IgG (ADA) vs time (FAS).

Figure 14.2.5 Mean Anti-imlifidase IgG (ADA) box plot

10 Change log

Version	Effective date	Reason for revision
1.0	12-May-2023	New document

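### The SAP's output list omits the Kaplan-Meier figures and the reason-for-graft-loss table that SAP section 4 requires, and titles the only graft-survival table as a proportion

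*SAP*

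**What the plan says.** SAP 4.4.1 settles the method: "The primary endpoint, overall graft survival at Year 3, will be analysed by the Kaplan-Meier survival method". It then promises the display, "The overall graft survival will be tabulated and presented graphically by treatment", and a further table: "The reason for graft loss will be tabulated by time". Its censoring rule covers "withdrawal from the trial without graft loss, evaluation time point and end of trial without graft loss". SAP 4.4.2.1 has Year 1 and Year 2 graft survival "analysed using the same methods as for the primary efficacy analysis". SAP 4.4.2.2 applies Kaplan-Meier to patient survival, again with a table and a graph by treatment. SAP 4.1.1 promises 95% confidence intervals in general. Protocol 12.3.1 asks for 95% confidence limits on the graft-survival table and graph, and the protocol synopsis names Kaplan-Meier curves.

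SAP section 9 opens with "The following sections contains lists of the tables, figures and listings (TLF) which will be produced". Its one graft-survival table is "Table 14.2.3 Proportion of patients with absence of graft loss at 1 year, 2 years and 3 years (FAS", and Listing 16.2.3 carries the same title. The figure list in 9.3 begins with "Figure 14.2.1 Individual plots DSA (including sum of DSA) vs time (FAS" and contains only plots of donor-specific antibodies (DSA) and anti-drug antibodies (ADA). SAP section 6, the place for deviations from the protocol analysis, reports the January 2023 termination and mentions no dropped output.

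**The concern.** A programmer working from section 9 would find no survival figure to build, and a graft-survival table whose title describes a simple proportion. A proportion and a Kaplan-Meier estimate agree when everyone is followed to the time point or to graft loss. They can differ when patients are censored earlier. The SAP is dated 12-May-2023, after the termination, so early censoring was foreseeable when the list was written. At stake are the primary endpoint's required display and, if Table 14.2.3 were built as titled, the primary number itself.

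**Working it through.** **1. Required outputs against listed outputs.** The documents contain no sample-size or power figure to reproduce, so the core check is a comparison of titles.

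| Required output | Source | In SAP section 9 |
|---|---|---|
| Kaplan-Meier graph, graft survival | SAP 4.4.1; protocol synopsis, 12.3.1 | 0 of 5 figures (2 DSA, 3 ADA) |
| Kaplan-Meier graph, patient survival | SAP 4.4.2.2 | 0 of 5 figures |
| Reason for graft loss by time | SAP 4.4.1; protocol 12.3.1 | 0 of 24 table titles |
| Kaplan-Meier table, graft survival | SAP 4.4.1, 4.4.2.1 | Table 14.2.3, titled as a proportion |
| Kaplan-Meier table, patient survival | SAP 4.4.2.2 | Table 14.2.8, method not named |

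Tables 14.2.1 to 14.2.8 and Figures 14.2.1 to 14.2.5 are numbered without a gap, so text lost in extraction or redaction is an unlikely explanation.

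**2. Can the two estimators differ under the SAP's own censoring rule?** Assume 20 patients with losses at 0.4, 0.9, 1.4 and 2.2 years, and 5 others censored at 1.2 years. After two losses and five censorings, 13 remain at risk. Kaplan-Meier at Year 3 is (19/20)(18/19)(12/13)(11/12) = 0.76. The proportion is 16/20 = 0.80 over all patients, or 11/15 = 0.73 over those with known Year 3 status. Without censoring, all three are 0.80. If the five are censored at 2.5 years, after the last loss, Kaplan-Meier is also 0.80.

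**3. How much censoring is plausible?** Protocol 3.2 plans the first visit for October 2020, one year after the first feeder-trial treatment, so treatment began about October 2019. From mid-October 2019 to 31 January 2023 is L = 39.5 months (38.5 to 1 January). Assumed, because the documents do not say: uniform accrual over A months, constant graft-loss hazard, no other dropout, and follow-up ending in January 2023. The lower end, A = 6, reflects that protocol 1.1 calls the feeder trial ongoing, with 180-day follow-up, and version 1.0 is dated 02-OCT-2020.

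Share unable to reach t months = 1 − min(1, (L − t)/A). With true 36-month survival S, hazard h = −ln(S)/36. If censored patients count as graft-free, bias = E[exp(−h·min(C, 36))] − S, where C is possible follow-up.

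Example with A = 18, L = 39.5, S = 0.70:
- h = 0.3567/36 = 0.00991 per month.
- Share not reaching 36 months = 1 − 3.5/18 = 81%.
- Expected reported proportion = (3.5/18)(0.70) + (1/18)(exp(−21.5h) − 0.70)/h = 0.136 + 0.606 = 0.743, so the bias is +4.3 points.

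| A (months), L = 39.5 | 6 | 12 | 18 | 24 | 30 |
|---|---|---|---|---|---|
| Cannot reach 36 months | 42% | 71% | 81% | 85% | 88% |
| Cannot reach 32 months (Year 3 window opens) | 0% | 38% | 58% | 69% | 75% |
| Bias at Year 3, S = 0.70 (points) | +0.4 | +2.1 | +4.3 | +6.5 | +8.9 |
| Bias at Year 2, S = 0.70 (points) | 0 | 0 | +0.1 | +1.2 | +2.9 |

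Over S = 0.60 to 0.80 and both end dates, the Year 3 bias runs from +0.3 to +12.3 points. For scale, the binomial standard error sqrt(0.7 × 0.3/n) is 10.2 points at n = 20 and 14.5 at n = 10, the anticipated arm sizes in protocol 12.6. A denominator of known Year 3 status, which neither document prescribes, would err the other way: at S = 0.70, L = 39.5 and a strict 36-month cut it reads 58% at A = 6, falling to 28% at A = 30.

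**4. What Kaplan-Meier does not repair.** It handles right-censoring. The Full Analysis Set (FAS) is patients enrolled in this trial (SAP 3.1), and protocol 3.1 says patients who lose the graft before entry do not continue, although the loss is recorded. If losses in the first 6 months fell outside the FAS, the curve would target 0.70^(30/36) = 74.3% where the truth is 70%, or +4.3 points. Whether they do is unclear.

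**The case against.** The strongest reply is that section 4 governs. It fixes the estimator, the censoring rule, and a table and graph by treatment, and nothing in section 9 prescribes another method. Section 9 gives titles without shells and is loose elsewhere: adverse-event table numbers 14.3.5, 14.3.8 and 14.3.9 are skipped, and the total IgG tables 14.2.6 and 14.2.7 have no counterpart in section 4. Table 14.2.3 may already be meant as Kaplan-Meier estimates at the three times, and reasons for graft loss might sit inside another output. SAP 4.1.1 covers confidence intervals and has all data listed by patient. SAP 4.2 gives completers by arm. Protocol 13.3 allows SAP changes to be described in the trial report. The trial is descriptive, has at most 30 patients and has already stopped.

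Most of this stands, and it rules out one tempting inference: that the sponsor replaced Kaplan-Meier with a crude proportion. The documents do not show that. It does not remove the mismatch. The survival figures are absent from the list, no title names the reason table, and protocol section 13 requires changes from protocol or SAP plans to be documented, yet SAP section 6 records none.

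**Conclusion.** The mismatch between section 9 and section 4 is certain and should be fixed. It is an unreconciled output list; the choice of analysis is sound.

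The consequence is conditional. Only if Table 14.2.3 were programmed as titled would the primary result be a crude proportion, and its bias cannot be sized from the documents. The +0.3 to +12.3 points rest on the accrual, hazard, dropout and cut-off assumptions above and on one choice of denominator. At 70% true survival the overstatement stays below the per-arm standard error throughout.

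Two further readings go too far. A reader might take the illustrated points as the bias in the reported result; the documents give no accrual, enrolment or event data to support that. A reader might also conclude that a Kaplan-Meier table makes the Year 3 figure unbiased; it deals with right-censoring only and leaves open any early losses outside the FAS. Harm is limited, since disposition tables and listings allow partial reconstruction, but the primary endpoint's required display is not on the production list.

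**What to change.** To deliver what the documents already require:
- Define Table 14.2.3 as the Kaplan-Meier estimates of SAP 4.4.1 at 12, 24 and 36 months by treatment, with 95% confidence limits.
- Label Table 14.2.8 as Kaplan-Meier.
- Add Kaplan-Meier figures by treatment for graft survival, with 95% confidence limits, and for patient survival.
- Add the table of reason for graft loss by time.

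If any of these was dropped on purpose, say so in section 6.

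Optional, and required by neither document: numbers at risk on the survival outputs, and a note in section 6 that termination shortens follow-up, with the number reaching Year 3 by treatment.

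The cost is two table labels, one table, two figures and perhaps a sentence or two, with no new data and no change of method or primary time point. The downside is slightly more output and a Year 3 estimate that is visibly imprecise. In the illustration at 70% survival and follow-up to 31 January, the expected number at risk at 36 months, n × min(1, 3.5/A) × 0.70, runs from 8.2 (A = 6) to 1.6 (A = 30) of 20 imlifidase patients, and from 4.1 to 0.8 of 10 plasma exchange patients.

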9.2 Listings

Listing 16.1.1 Patient disposition, including reason for discontinuation (All screened patients).

Listing 16.1.2 Protocol Deviations (FAS).

Listing 16.1.3 Demography and body measurements (FAS).

Listing 16.1.4 Medical and surgical history (FAS).

Listing 16.1.5 Concomitant medication (FAS).

Listing 16.1.6 Previous transplant kidney history (FAS).

Listing 16.2.1 MFI levels for DSA – by time point (FAS).

Listing 16.2.2 Kidney function (based on S/P-creatinine analysis) (FAS).

Listing 16.2.3 Proportion of patients with absence of graft loss at 1 year, 2 years and 3 years (FAS).

Listing 16.2.4 Proportions of patients with presumed or biopsy proven AMR episodes (FAS).

Listing 16.2.5 Proportion of patients with presumed or biopsy-proven rejection episodes, (other than AMR episodes) (FAS).

Listing 16.2.6 Total IgG – by timepoint (FAS).

Listing 16.2.7 Proportion of patients having reduction in total IgG (FAS).

Listing 16.2.8. Patient survival (FAS).

Listing 16.3.1 AEs (FAS).

Listing 16.3.2 AEs – by SOC and PT (FAS).

Listing 16.3.3 Serious adverse event SAEs (FAS).

Listing 16.4.1 Clinical chemistry variables (U-Albumin, Creatinine, U-Albumin/creatinine ratio) – by time point (FAS).

Listing 16.4.2 Anti imlifidase IgG (ADA) (mg/mL) – by time point (FAS)

9.3 Figures

Figure 14.2.1 Individual plots DSA (including sum of DSA) vs time (FAS).

Figure 14.2.2 Mean plots of sum of DSA vs time (FAS).

Figure 14.2.3 Individual Anti-imlifidase IgG (ADA) vs time (FAS).

Figure 14.2.4 Mean Anti-imlifidase IgG (ADA) vs time (FAS).

Figure 14.2.5 Mean Anti-imlifidase IgG (ADA) box plot

10 Change log

Version	Effective date	Reason for revision
1.0	12-May-2023	New document
